#### 8.3 Visit 3: One day after the Cataract Surgery (Day 1)

- 1. Vital signs
- 2. Assessment of Adverse Events
- 3. Assessment of any concomitant medication
- 4. Assessment of ocular pain
- 5. Slit Lamp Examination
- 6. Assessment of intraocular pressure
- 7. Administration of the study drug to the operated eye (Administration of study drug should only be performed by the patient, caregiver, independent study drug administrator or unmasked site personnel that are not assigned any other study duties)
- 8. Re-dispense the subject diary to the subject with instructions to document the administration of the study drug, adverse events, and any concomitant medication used. Also, the patient should be instructed to administer the study medication before visiting the clinical facility for next scheduled visit.
- 9. Schedule Visit 4

#### 8.4 Visit 4: Follow-up Visit (Day $7 \pm 2$ Days)

- 1. Review the subject diary to assess for any adverse events, changes in concomitant medication & compliance to study drug.
- 2. Retrieve the subject diary pages for completed visit and keep in the source file of the patient
- 3. Vital signs
- 4. Assessment of ocular pain
- 5. Visual acuity assessment
- 6. Slit Lamp Examination
- 7. Assessment of Intraocular pressure
- 8. Re-dispense the subject diary to the subject with instructions to document the administration of the study drug, adverse events, and any concomitant medication

used. Also, the patient should be instructed to administer the study medication before visiting the clinical facility for next scheduled visit.

9. Schedule Visit 5

#### 8.5 Visit 5: End of Study Visit/Early Discontinuation Visit (Day 14 ± 2 Days)

- 1. Review of subject diary card to assess if any adverse events, changes in concomitant medication & compliance to study drug.
- 2 Retrieve the subject diary pages for completed visit and keep in the source file of the patient
- 3. Collect the study medication container from the subject.
- 4. Physical Examination and Vital signs. At a minimum, the physical examination will include the following: assessment of general appearance, skin, HEENT, heart, lungs, musculoskeletal system, lymph nodes, neurological systems, gastrointestinal system, genitourinary system and extremities.
- 5. Assessment of ocular pain
- 6. Visual acuity assessment
- 7. Slit Lamp Examination
- 8. Assessment of Intraocular pressure
- 9. Fundus Examination
- 10. Urine Pregnancy Test (for females of child bearing potential)
- 11. The laboratory evaluation for routine hematology, biochemistry and urine analysis.
- 12. A standard of care treatment may be advised at the Investigator's discretion.

#### 8.6 Unscheduled Visits and Early Discontinuation Visit:

An Unscheduled Visit is allowed at any time, for any reason, if in the Investigator's opinion it is warranted. If the Unscheduled Visit is due to an AE, the Investigator will determine whether additional visits are needed.

If a study subject is discontinued from the study during an Unscheduled Visit, the Unscheduled Visit will be referred to as an Early Discontinuation Visit and all procedures scheduled for Visit 5 will be performed. If the Unscheduled Visit is not an Early Discontinuation Visit (i.e., the study subject will continue to take part in the study), then the reason for unscheduled visit is documented and required procedures at the discretion of CONFIDENTIAL Page 27 of 63 investigator considering the reason for visit, will be performed.

If the study subject's condition has worsened to the degree that it is unsafe for the study subject to continue in the study, the study subject may be discontinued from the study as treatment failure and a standard of care treatment may be advised at the Investigator's discretion.

#### 9.0 STUDY SUBJECT DISPOSITION AND DISCONTINUATION

Study subjects will be discontinued from the study for any of the following reasons:

- If the study subject withdraws his or her consent for any reason
- Subjects whose condition worsens and require alternate or supplemental therapy for the treatment of inflammation and pain the subject should be discontinued, excluded from the PP population analysis, and provided with effective treatment
- If the study subject's drug code is unmasked
- If an adverse event occurs for which the study subject desires to discontinue treatment or the Investigator determines that it is in the study subject's best interest to be discontinued
- If there is a protocol violation\*
- If a concomitant therapy is reported or required which is prohibited or may interfere with the results of the study
- If the study subject misses 3 consecutive days' IP applications or has made less than 14 or more than 20 product administrations in the study
- If the study subject is lost to follow-up
- If the study subject becomes pregnant
- Administrative reasons
- Any other reason that may affect the outcome of the study or the safety of study subjects

\*A protocol violation is defined as any study subject or Investigator activity that could have possibly interfered with the therapeutic administration of the treatment or the precise evaluation of treatment efficacy that affects the rights, well-being or safety of the subject or the scientific integrity of the study data.

The reasons for a study subject discontinuation will be documented. If a study subject is discontinued from the study for any reason, the procedures scheduled for Visit 5 will be completed and any outstanding data and study drug will be collected if possible. Data, in addition to the reason for discontinuation and the date of removal, will be documented on the End of Study Case Report Form.

Before a study subject is considered to be lost to follow-up, the Investigator will document all attempts to reach the study subject twice by telephone and will send a certified follow-up letter.

In the event that a study subject discontinues from the study at any time due to an adverse event, the reason for discontinuation, the nature of the event and its clinical course must be fully documented. For such a study subject, the Investigator must strive to follow the study CONFIDENTIAL Page 28 of 63

subject until the adverse event has resolved, become clinically insignificant, is stabilized or the study subject is lost to follow-up. Should a Serious Adverse Event be noted, procedures stated in section 13.2 must be followed.

When a study subject discontinues the study due to any of the above reasons, the study subjects should be prescribed appropriate treatment that he/she can continue to use as per the Investigators clinical judgment.

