#### TEST OF EQUIVALENCE:

• The PP population includes all randomized subjects who meet all inclusion and exclusion criteria,

• The safety population includes all randomized subjects who receive study drug.

Subjects who discontinue because of lack of treatment effect after completing two days of treatment should be analyzed in the mITT and PP populations as a treatment failure. Subjects discontinued for other reasons, including drug-related adverse events, should be excluded from the PP population, but included in the mITT population using Last Observation Carried Forward (LOCF).

The recommended primary endpoint is the proportion of subjects with cure at Visit 5 (end of the study on day  $14 \pm 2$  days) defined as a score of 0 for aqueous cells, a score of 0 for aqueous flare and a score of no more than 3 for pain.

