### 3.0 STUDY OVERVIEW

Approximately 450 subjects **and are planning**, subjects who have a cataract and are planning to undergo cataract surgery will be enrolled and randomized in this investigational study.

One drop of the suspension should be instilled into the affected eye one-time daily, beginning a day prior to the planned cataract surgery, on the day of the cataract surgery, and for 14 days thereafter. On the day of cataract surgery (day 0) a drop should be added 30-120 minutes prior to the surgery and an additional drop will be administered following cataract surgery prior to the subject leaving the surgery center. The study is designed to be only monocular (only one eye per subject).

The dose and mode of treatment chosen in this study is the dosage approved by US FDA for the treatment of pain and inflammation associated with cataract surgery.

The study subjects will undergo clinical evaluations throughout the study in order to assess efficacy and safety. Study subject primary endpoint evaluation will be assessed on Visit 1 (-21 to -1 Days prior to cataract surgery), Visit 3 (Day after the cataract surgery), Visit 4 (Follow up Visit Day  $7 \pm 2$  days) and Visit 5 (End of study Day  $14 \pm 2$  days).

If the Investigator determines that the study subject's condition has worsened to the degree that it is unsafe for continuation in the study, the study subject may be discontinued and will be evaluated as a treatment failure.

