#### 4.4 **Prohibitions:**

The following are prohibited during the study:

- a. Ophthalmic prostaglandin analogs, e.g., bimatoprost (Lumigan®), latanoprost (Xalatan®) or travoprost (Travatan®, Travatan Z®).
- b. Topical, ophthalmic, e.g. cyclosporine (Restasis®) and lifitegrast (Xiidra®), inhaled or systemic NSAIDs, other than the assigned study drug.
- c. Topical, ophthalmic, or systemic corticosteroid.
- d. Use of systemic analgesic medications, e.g. narcotics, tramadol, Neurontin®Intraocular corticosteroid implant.
- e. Intravitreal or subtenon injection of ophthalmic corticosteroid.
- f. High-dose salicylate therapy (>81mg/day).
- g. Medications which may prolong bleeding time (e.g. Warfarin®, Eliquis®) should be evaluated on a case-by-case basis by the investigator to determine if the subject is eligible to participate.
- h. Contact lenses in the operative eye. Contact lens use in the non-operative eye is acceptable.
- i. Ocular surgery in the study eye, other than study surgery.

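### Protocol 9.0 removes from the PP population a worsening subject whom the Synopsis keeps there as a treatment failure after two days of treatment

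*Protocol*

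**What the plan says.** Two passages of the protocol set the PP status of a subject who stops because the treatment is not working.

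- **Protocol 9.0, list of discontinuation reasons.** The worsening bullet applies to subjects who "require alternate or supplemental therapy for the treatment of inflammation and pain the subject should be discontinued, excluded from the PP population analysis". It sets no minimum time on treatment.
- **Synopsis, Test of Equivalence.** "Subjects who discontinue because of lack of treatment effect after completing two days of treatment should be analyzed in the mITT and PP populations", and they count there as failures. The next sentence gives the remainder rule: "Subjects discontinued for other reasons, including drug-related adverse events, should be excluded from the PP population", with mITT handled by last observation carried forward.

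Three further places deal with worsening that makes it unsafe to continue, and none names a population. In Protocol 3.0, and in the same terms in SAP 3.1, "the study subject may be discontinued and will be evaluated as a treatment failure". In Protocol 8.6, "the study subject may be discontinued from the study as treatment failure".

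Equivalence is tested in PP only (Protocol 12.9; SAP 6.3 and 7.7.1.1). The two-sided, continuity-corrected 90% confidence interval for Test minus Reference must lie within ±0.20. SAP 8 declares no change from the protocol's analyses. Most of the PP definition in SAP 6.3 and a block in SAP 7.7.1 are redacted.

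**The concern.** The study drug is given to treat pain and inflammation after surgery. A subject who gets worse on it and needs something else for the same pain and inflammation is the plainest case of lack of effect. If that happens after two days of treatment, Protocol 9.0 takes the subject out of PP and the Synopsis keeps the subject in PP as a failure. Neither passage refers to the other.

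At stake is a set of subjects who are failures almost by definition. Following 9.0 removes failures, and only failures, from the population that decides equivalence. If the two products differ in how often rescue is needed, those failures are part of the evidence about that difference. If the choice between the rules were left until after unmasking, it could be made with the result in view.

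**Working it through.** **1. The rules side by side**, for a subject who worsens, needs other therapy for pain and inflammation, and is discontinued after at least two days of treatment:

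| Place | Status |
|---|---|
| Protocol 9.0, worsening bullet | Excluded from PP |
| Synopsis, lack of effect | Failure in PP and mITT |
| Protocol 3.0, Protocol 8.6, SAP 3.1 | Treatment failure, population not named |

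Before two days the rules can agree. Lack of effect is not itself on the 9.0 list. The same subject might also be recorded under "If a concomitant therapy is reported or required which is prohibited or may interfere with the results of the study", since the prohibitions in Protocol 4.4 include "Topical, ophthalmic, or systemic corticosteroid" and "inhaled or systemic NSAIDs, other than the assigned study drug". That bullet states no PP consequence, but the Synopsis remainder rule could then exclude the subject.

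**2. Inputs for the size.** The plan has no figure to reproduce: it gives no rate for these discontinuations, and allocation is redacted. Assumed: 160 PP subjects per active arm; Reference cure 62%, near the label's 61% to 65% inflammation resolution at Day 14 (Protocol Appendix III); every affected subject a failure if kept.

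**3. Formulas.** If a share k of an arm is removed and all are failures, PP cure moves from p to p/(1−k). The interval is d ± [1.645·SE + (1/nT + 1/nR)/2]. For example, at 10% Test v 2% Reference with true cure 42% v 62%: 0.42/0.90 − 0.62/0.98 = 0.467 − 0.633 = −0.166, in place of −0.200.

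**4. Simulation (2,000,000 trials): probability of concluding equivalence.**

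| Affected, Test v Reference | True difference −20 points: kept → excluded | True difference 0: kept → excluded |
|---|---|---|
| 2% v 2% | 3.9% → 3.2% | 94.5% → 94.5% |
| 3% v 2% | 3.9% → 3.8% | 94.5% → 94.3% |
| 5% v 5% | 3.9% → 2.5% | 94.5% → 94.4% |
| 5% v 2% | 3.9% → 5.4% | 94.5% → 92.8% |
| 10% v 2% | 3.9% → 12.1% | 94.5% → 80.9% |

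For 130 to 180 per arm, the 12.1% ranges from 10.7% to 12.9%.

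**5. A second parameterisation.** Remove the same share f of failures from each arm, so that PP cure is p/[p + (1−p)(1−f)]. Exact enumeration used 150 or 180 per arm, Reference cure 61% or 65%, and Test 20 points lower. False equivalence is 3.5% to 3.9% at f = 0, 4.0% to 4.2% at 10%, 4.5% to 5.5% at 25%, and 8.1% to 12.4% at 50%. The sign differs from the equal-rate rows above because an equal share of failures takes more subjects from the weaker arm. At f = 25% and cure 41% v 61%, the shares removed are 0.25 × 0.59 = 14.8% and 0.25 × 0.39 = 9.8%.

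**6. Direction with no imbalance in cells and flare.** Suppose need for rescue is independent of cell and flare outcome (63% in both arms) and affects 10% v 2%. Kept cure is 0.63 × 0.90 = 56.7% v 0.63 × 0.98 = 61.7%. Equivalence is then concluded in 83% of trials if these subjects are kept and 93% if they are excluded. In the last row of the table, with equal overall cure, exclusion lowered that probability.

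**7. A borderline case.** 82/160 v 99/160 gives −20.3 to −0.9 points (not equivalent). Excluding 5 Test and 3 Reference failures, 82/155 v 99/157 gives −19.9 to −0.4 (equivalent).

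**The case against.** The strongest reply is that the deciding text cannot be read. SAP 6.3 shows one PP criterion and then redacted bullets, SAP 7.7.1 has a redacted block just after the cure and failure definitions, and SAP 7.5 points to a separate deviations list. Protocol 12.0 makes the SAP the working record of the statistical evaluation, so a disposition bullet in 9.0 may not control PP membership at all. This stands. A reader might infer that the primary analysis is unresolved, and the documents do not support that. What they show is a conflict in the visible rules, and redacted SAP text cannot correct the wording of 9.0.

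It can also be said that worsening and lack of effect are different things. The documents draw no such line, and Protocol 3.0 and 8.6 call unsafe worsening a treatment failure.

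A reader might infer that sites will record these subjects under the bullet that excludes them. The case report form's reason list is not in the documents, 9.0 has a catch-all reason, and 8.6 lets the investigator discontinue a subject directly as a failure.

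A reader might also infer that SAP 7.8.9 removes early failures anyway. A last dose on Day 10 means 10 + 3 = 13 doses and 14 − 10 = 4 missed days, over its limit of 3 consecutive days. That reading joins two separate sentences: the 16-day window defines the number of missed doses, and the exclusion does not say that doses planned after discontinuation count. A reading consistent with the Synopsis is available.

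The borderline case is a knife-edge. One more Test cure (83/160) gives a lower limit of −19.7 with nobody excluded, and excluding 5 and 5, or 5 and 4, failures does not change the conclusion. Masking of site staff, monitors and data analysts (Protocol 11.4) limits arm-directed handling. Superiority uses mITT and is untouched by a PP exclusion.

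**Conclusion.** The conflict is real, and 9.0 is the passage that should give way. It excludes from the only equivalence population subjects whom the Synopsis counts there as failures, and it disagrees in spirit with Protocol 3.0, Protocol 8.6 and SAP 3.1.

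The likely size is small. With equal rates of affected subjects in both arms, the effect is negligible or slightly conservative. With an equal share of failures removed, it stays small up to about 25% of failures. At 5% v 2%, false equivalence rises by 5.4 − 3.9 = 1.5 points. It is large only at an assumed imbalance such as 10% v 2%, for which the documents offer no support. All of this rests on assumed rates, arm sizes and cure rates.

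A reader might infer that the exclusion biases the trial toward a claim of equivalence. The documents do not support a direction: it changes with whether the arms lose equal shares of subjects or of failures, and with how rescue relates to cell and flare outcome. The reason to act is that the rule is wrong as written and cheap to correct before unmasking.

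**What to change.** In the Protocol 9.0 worsening bullet, replace the words on PP exclusion with: *analysed as a treatment failure in the PP and mITT populations if discontinued after completing two days of treatment*. Discontinuations before two days are not in dispute, and the bullet can keep them out of PP if it says so.

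If the redacted text of SAP 6.3 and 7.7.1 does not already do this, add one sentence there: such subjects are PP failures, and doses planned after the discontinuation do not count as missed under SAP 7.8.9.

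The cost is one phrase and at most one sentence. PP cure rates fall slightly because a few exclusions become failures: with 2% affected, 0.62/0.98 = 63.3% becomes 62.0%.

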#### **11.7 Assessment of Compliance**

A subject diary will be provided to all subjects where it is required to document the date and time of administration of the study drug. In the subject diary, subjects will also note any adverse event observed and any concomitant medication taken or changes.

Compliance will be determined from the subject diary, which the subject will be trained and instructed to use to record all doses, as well as all missed doses. The number of missed and additional doses will be captured on the compliance page of the CRF.

Subject who misses 3 consecutive doses of study medication will be considered noncompliant and discontinued from the study. The used kits of study medication will be returned to the study site at appropriate visits or early termination or as applicable.

Subject who will take less than 14 doses of total study drug during the study will be considered non-compliant and discontinued from the study. Subjects who will take more than 20 doses of the study drug are also considered as non-compliant and discontinued from the study.

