#### **12.9 Test of Bioequivalence**

For the primary efficacy parameter, i.e. the proportion of patient(s) in the per protocol population identified as "treatment success" occurring at Visit 5 (end of the study on day  $14 \pm 2$  days)., a two-sided 90% confidence interval for the difference in success proportions  $(P_T - P_R)$  between test and reference products should be contained within [-0.20, +0.20] in order to establish equivalence.

The above analyses of therapeutic equivalence will be performed for the per-protocol population.

The detailed description of the statistical analysis to be used for the statistical evaluation & construction of 90% confidence interval will be elaborated in the Statistical Analysis Plan (SAP).

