7.8.9 Exposure to Product

The subjects will be instructed to use the diary to document all doses taken. Additionally, the dose taken one day prior to the surgery will be recorded on the eCRF.

Compliance with scheduled application of IP will be determined from the subject's diary as $[\text{Actual number of doses}] / [\text{Planned number of doses}] * 100\%$, where

- Actual number of doses will counted from the subject diary and relevant eCRF pages;
- Planned number of doses is 17 (i.e. Days -1 through Day 14 with two doses taken on Day 0).

Number of missed doses will be calculated as the number of planned dosing time-points when the study drug was not taken during the 16 days starting with the date of the first dose. There is one dosing time-point per each day, except the day of Visit 2 Day 0, when there are two planned time-points, before the surgery and after the surgery.

Subjects who missed dosing for more than 3 consecutive days will be considered non-compliant and will be excluded from the PP population.

Subjects can be additionally excluded from the PP population due to non-compliance, if the Investigator's and Sponsor's review of their dosing times suggests a clinically meaningful departure from the once-daily dosing pattern.

Subjects will be considered compliant if they administer at least 14 doses and not more than 20 doses, with no more than 3 consecutive missed dosing days. The compliance will be analyzed using the descriptive statistics by treatment group. The proportion of compliant vs. non-compliant subjects will be tabulated for each treatment.

Duration of exposure will be calculated as Date of last use of the study drug – Date of first use of the study drug + 1. Duration of exposure will be summarized descriptively by treatment group.

Compliance, number of doses and duration of exposure will be summarized for the Safety and mITT populations.

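### Protocol 9.0 removes from the per-protocol set subjects who worsen and need other therapy, while the synopsis keeps lack-of-effect discontinuations after two days in it as failures

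*Protocol*

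**What the plan says.** Four parts of the plan bear on the PP status of a subject who does badly and stops early.

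- **Protocol 9.0 (discontinuation list).** A subject who worsens and needs other treatment for inflammation and pain: "the subject should be discontinued, excluded from the PP population analysis, and provided with effective treatment". There is no time limit.
- **Protocol synopsis, Test of Equivalence.** Subjects who stop for "lack of treatment effect after completing two days of treatment should be analyzed in the mITT and PP populations as a treatment failure". Those who stop for other reasons, drug-related adverse events included, leave PP and stay in mITT with LOCF.
- **Protocol 3.0, Protocol 8.6 and SAP 3.1.** If worsening makes continuation unsafe, "the study subject may be discontinued and will be evaluated as a treatment failure" (3.0, and the same in SAP 3.1) or "the study subject may be discontinued from the study as treatment failure" (8.6). None of the three names PP.
- **Compliance rules.** Protocol 9.0 also discontinues a subject who "has made less than 14 or more than 20 product administrations in the study". Protocol 11.7 says: "Subject who will take less than 14 doses of total study drug during the study will be considered non-compliant". SAP 7.8.9 says: "Subjects who missed dosing for more than 3 consecutive days will be considered non-compliant and will be excluded from the PP population". SAP 7.8.9 plans 17 doses and counts missed doses over a fixed 16 days from the first dose.

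On the population for equivalence, Protocol 12.9 says: "The above analyses of therapeutic equivalence will be performed for the per-protocol population". SAP 6.3 and 7.7.1.1 agree. SAP 8 declares no change from the protocol's analyses.

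**The concern.** Protocol 9.0 and the synopsis assign opposite PP status to the same subject. In the 9.0 list, worsening is the only reason tied specifically to efficacy; lack of effect has no entry of its own. If that entry removes subjects from PP, the synopsis rule has almost nobody left to apply to.

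The 9.0 rule also selects the primary population on outcome, because the subjects it removes are those doing badly. If more of them are on one product, the removal hides part of the difference that the test is meant to detect. If the text is left unresolved, someone must choose between the rules later, in the population that decides equivalence.

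The compliance rules add to this. Even with 9.0 corrected, a subject who stops early for lack of effect will have few doses and a run of days without dosing, and the visible SAP text makes no exception.

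**Working it through.** **1. One subject under each rule.** Take a subject who doses as planned, worsens on Day 5 and stops for other therapy.

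| Text | Status |
|---|---|
| Protocol 9.0 | out of PP |
| Synopsis | in PP and mITT as a failure |
| Protocol 3.0, 8.6, SAP 3.1 (if unsafe to continue) | failure, PP not named |
| SAP 7.8.9 | out of PP if the remaining days count as missed |

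**2. Dose count.** The planned total in SAP 7.8.9 reproduces: 1 (Day -1) + 2 (Day 0) + 14 (Days 1 to 14) = 17. For a fully adherent subject with last dose on Day d (d at least 0):

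- doses = 1 + 2 + d = 3 + d
- planned days missed = 14 - d

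| Last dose | Doses | Days missed in a row | Below 14 doses | SAP, more than 3 days |
|---|---|---|---|---|
| Day 0 | 3 | 14 | yes | yes |
| Day 5 | 8 | 9 | yes | yes |
| Day 10 | 13 | 4 | yes | yes |
| Day 11 | 14 | 3 | no | no |
| Day 14 | 17 | 0 | no | no |

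Every early failure whose last dose is on or before Day 10 meets both conditions. On Day 11 the subject misses exactly 3 days. That meets the limit of 3 in Protocol 9.0 and 11.7 but not the SAP's limit of more than 3.

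**3. Effect on the equivalence test.** The documents show neither arm sizes nor removal rates, so this part is illustrative.

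- Assumed reference cure: 63%, within the 61-65% Day 14 inflammation resolution in the label (Protocol Appendix III).
- Assumed test cure: 43%, at the -20 point limit, so any declaration of equivalence is false.
- Assumed arm size: n = 120, 150 or 180. All removed subjects are failures.
- Decision rule (SAP 7.7.1.1): the continuity-corrected 90% interval lies within ±0.20. The half-width is 1.645 × SE + 0.5 × (1/nT + 1/nR).

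If a share r of an arm is removed, its PP cure rate becomes p/(1 - r). For 5% of reference and 10% of test: 0.63/0.95 = 66.3%, 0.43/0.90 = 47.8%, gap -18.5 points. If the same share of failures is removed in each arm, rT = rR × 0.57/0.37, so 5% goes with 7.7% and 10% with 15.4%.

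Simulation with 1,000,000 trials per scenario:

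| Removed, reference v test | PP gap (points) | False equivalence, n = 120-180 |
|---|---|---|
| none (kept as failures) | -20.0 | 3.5-3.8% |
| 5% v 5% | -21.1 | 2.4-2.5% |
| 10% v 10% | -22.2 | 1.4-1.6% |
| 5% v 7.7% (proportional) | -19.7 | 4.0-4.3% |
| 10% v 15.4% (proportional) | -19.2 | 4.7-5.3% |
| 5% v 10% | -18.5 | 5.8-6.7% |
| 5% v 15% | -15.7 | 12-16% |

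Hand check at n = 150, by the normal approximation: z = 1.645 + (c - 0.20 - gap)/SE, where c is the continuity term and the gap is a signed proportion.

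- Kept: 1.645 + 0.0067/0.0565 = 1.763, giving 3.9%.
- 5% v 10%: 1.645 + (0.0072 - 0.0146)/0.0584 = 1.518, giving 6.4%.

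Sensitivity with reference cure 61% or 65% and test 20 points lower (n = 120 and 180):

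- kept: 3.8-3.9%
- proportional removal: 3.8-4.6% (5% of reference) and 4.3-6.0% (10% of reference)
- 5% v 10%: 5.6-7.0%

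**4. Power when both products cure 63%**, with 5% or 10% removed from each arm:

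| n per arm | Kept | Removed |
|---|---|---|
| 120 | 84.6% | 84.4% |
| 150 | 93.6% | 93.0% |
| 180 | 97.2% | 97.0-97.1% |

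The largest difference on these rounded figures is 93.6 - 93.0 = 0.6 point.

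**The case against.** **Separate groups.** Worsening that needs other therapy could be read as distinct from lack of treatment effect, which would make the defect an undefined boundary and not a contradiction. Nothing in the visible text draws that boundary, and the 9.0 list has no separate lack-of-effect entry, so the clash stands.

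**Failure without PP.** Protocol 3.0, 8.6 and SAP 3.1 do not name PP. A subject can be a failure in mITT and be absent from PP. This is correct: those sections lean towards the synopsis but do not settle PP status. The direct conflict is between 9.0 and the synopsis.

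**Redaction.** Most PP criteria in SAP 6.3 and a block of SAP 7.7.1 are blacked out, and the PP definition in Protocol 12.4 is incomplete as released. Hidden text may say which rule governs or exempt failures from the compliance rules. This limits the compliance part most. In addition, the visible text ties fewer than 14 doses to discontinuation and not directly to PP exclusion; only the consecutive-days rule names PP. Whether days after a directed stop count as missed is also a matter of reading, although the SAP's fixed 16-day window supports counting them. No hidden text removes the conflict between the two visible protocol statements.

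**Other routes out of PP.** The same subject might be recorded under prohibited therapy (9.0, 13.8) or as an adverse event. This is a fair addition to the repair, not an argument against it.

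**Small effect.** Under equal removal the 9.0 rule is conservative, and under proportional removal the error stays near 5%. This stands, and the point does not depend on a shown bias.

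**Conclusion.** The concern holds. For a subject who worsens and stops for other therapy after two days of treatment, Protocol 9.0 and the synopsis give opposite status in the only population used for equivalence, and no visible SAP text decides between them. The compliance rules, read literally, would also remove any such subject whose last dose is on or before Day 10. That part is conditional on the redacted text.

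No direction of bias is established. Under the stated assumptions, false equivalence stays at or near 5% unless clearly more test than reference subjects are removed, and the power cost of either rule is about half a point. This should be fixed because the rule decides who is in the primary analysis and can be settled cheaply in advance.

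**What to change.** Before unmasking, and as analysis classification only:

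1. In Protocol 9.0, replace the PP exclusion for worsening subjects with the synopsis classification: a subject discontinued for lack of treatment effect after two days of treatment is a failure in PP and mITT. Say that worsening leading to other therapy falls under it however the stop is coded, and state the PP status of subjects who worsen before completing two days.
2. State in Protocol 11.7 or 12.4 and in SAP 7.8.9 that subjects kept as failures are not removed from PP solely because stopping left them with fewer than 14 doses or with missed dosing days.
3. Check that Protocol 12.4 and SAP 6.3, 7.7.1 and 7.8.9 agree, and reconcile the protocol's limit of 3 consecutive missed days with the SAP's limit of more than 3.

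No rescue, stopping or dosing rule changes.

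**Cost.** Short wording edits and a consistency check, with no new data, visits or subjects. PP will include some subjects with few doses, and PP cure rates will be lower: 63%, against 0.63/0.95 = 66.3% if 5% would have been removed or 0.63/0.90 = 70% if 10%. Precision hardly changes: the mean half-width of the 90% interval at equal 63% cure is 11.0 points kept v 11.1 removed at 120 per arm, 9.8 v 9.9 at 150, and 8.9 v 9.0 at 180.
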